#### **5.4. Secondary Immunogenicity Endpoint(s) Analysis**

Key secondary endpoints (for Cohorts 1 and 2) include F protein binding antibodies (pre-F and/or post-F), and antigen-specific T-cell responses (as defined by IFN- $\gamma$  ELISpot).

The data on titers of F protein binding antibodies for RSV-A and RSV-B and antigen-specific T-cell responses will be analyzed similarly as described in Section 5.3.3 but using log2 or log10 transformation as applicable. For ELISpot, only the following descriptive statistics will be calculated: N, median, quartiles, minimum and maximum.

## 5.5. Exploratory Endpoints Analysis

Exploratory endpoints may include the following, but are not limited to: RSV neutralization antibody titers against additional A and/or B strains, anti-F protein antibody specificity and functionality characterization, adenovirus neutralization antibody titers, molecular antibody characterization (eg, avidity, Fc cell interaction, antibody-dependent cell-mediated cytotoxicity [ADCC], antibody-dependent cell-mediated phagocytosis [ADCP], antibody isotyping, antibody sequencing for repertoire), including but not limited to immunoglobulin (Ig)A and IgG, chemokines and cytokines in serum samples, transcriptome analysis and sequencing of the T-cell receptor (TCR) and/or B-cell receptor (BCR) or heavy/light chain (VH/VL) characterization, evaluation of the cellular immune response and the functional and memory immune response by intracellular cytokine staining (ICS), cellular phenotyping and memory B-cell ELISpot.

Scatterplot with humoral and cellular assays may be provided for the most important time points. Alternatively, in case of no quantitative data available or in case of sparse data, the results may be summarized by frequency and proportions along with 95 CIs.

### 5.5.1. ICS

For ICS, if available, analyses may include:

Total Cytokine response: the % of subsets expressing at least IFN $\gamma$ , TNF $\alpha$  or IL2 will be calculated for CD4 and CD8 separately (IFN $\gamma$  and/or TNF $\alpha$  and/or IL2). Here, at least one cytokine should be positive. For total cytokine responses, tables with number of observations, median, first and third interquartile per timepoint will be provided. Subject profiles of the actual values over time will be graphically presented. Actual values are shown as box plots with dots for subject values, and the corresponding median and the first and third quartile (Q1, Q3) per time point.

Total CD8 cytotoxic response: the % of subsets expressing cytotoxic markers such as Perforin, Granzyme B and/or CD107a will be calculated for CD8. Tables with number of observations, median, first and third interquartile per timepoint will be provided. Subject profiles of the actual values over time will be graphically presented. Actual values are shown as box plots with dots for subject values, and the corresponding median and the first and third quartile (Q1, Q3) per time point.

Polyfunctionality analysis will be assessing the possible cytokine combinations with at least one cytokine being positive (for example, IFN $\gamma$ +TNF $\alpha$ + IL2+, IFN $\gamma$ +TNF $\alpha$ +IL2-, IFN $\gamma$ +TNF $\alpha$ -IL2- etc). For the polyfunctionality analysis bar charts reflecting the median magnitude and/or the mean $\pm$ SD of each combination may be graphically presented. In that case, tables with the corresponding descriptive statistics will also be provided.

**Th1 and Th2:** Th1 is defined as all CD4+ IFN $\gamma$  and/or TNF $\alpha$  and/or IL2 and Th2 as all CD4+ as IL4 and/or IL13 and CD40L+ cells. Subject profiles and graphs of the actual values over time (box-plot type including individual scatterplots) will be created. In addition, at time points of interest, scatterplots of Th1 vs Th2 might be created. For the graphs, original values will be displayed on the log10 scale.

The technical details for the calculation of the ICS values to be used in the graphs will be outlined in the data presentation specifications (DPS) document.

### **5.5.2. VNA against Ad26 vector**

For VNA against the Ad26 vector, if available following statistics will be calculated: N, geometric mean and corresponding 95% CI of the actual values. Subject profiles of the assays against the insert (RSV-A and RSV-B) will be repeated, highlighting subjects with pre-existing immunity at baseline against the vectors. Scatterplots of the Adeno assay versus the assays against the inserts may be provided for the most important time points. In these scatterplots the actual values will be shown, even if they are below the LLOQ.

### **5.6. Handling of Missing and/or Unquantifiable Immune Response Data**

Missing immune response data will not be imputed. Values below the lower limit of quantification (LLOQ) will be imputed based on the type of analysis:

- For the calculation of the geometric mean titer, values below LLOQ will be imputed to LLOQ/2. While for the calculation of the geometric mean of the increase from baseline, values below LLOQ will be imputed to LLOQ.
- Data above the ULOQ will be imputed with the ULOQ.

The ULOQ and LLOQ values per assay will be available in the database.

For ICS: if no LLOQ is available at the time of analysis, a provisional lower limit will be used to impute as described above. The provisional lower limit will be provided in the data base.

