Under normal circumstances, the blind must not be broken for a cohort until all participants in that cohort have completed the study and the database is finalized for the cohort, except for Cohort 3: the blind will be broken for participants in Arms 10 and 13 once all participants in these arms have completed their last visit after 1 year of follow-up post-vaccination. The investigator may, in an emergency, determine the identity of the randomization group by contacting the IWRS. While the responsibility to break the intervention code in emergency situations resides solely with the investigator, it is recommended that the investigator contact the sponsor or its designee if possible, to discuss the particular situation, before breaking the blind. Telephone contact with the sponsor or its designee will be available 24 hours per day, 7 days per week. In the event the blind is broken, the sponsor must be informed as soon as possible. The date, time, and reason for the unblinding must be documented by the IWRS, in the appropriate section of the eCRF, and in the source document. The documentation received from the IWRS indicating the code break must be retained with the participant's source documents in a secure manner.

Participants who have had their intervention assignment unblinded should continue to return for scheduled evaluations.

In general, randomization codes will be disclosed fully only if the study is completed and the clinical database is closed. However, if an interim analysis is specified (Section 9.5), the randomization codes and, if required, the translation of randomization codes into vaccine and control groups will be disclosed to the sponsor and only for those participants included in the interim analysis.

Participants who withdraw will not be replaced.

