### 9.2.4. Revaccination and Durability Cohort (Cohort 4)

The revaccination and durability cohort (Cohort 4) should provide sufficient data on the selected vaccine formulation to support future clinical development. To have approximately 150 participants available per arm for evaluating durability of immune response at end of the 5-year study period, and assuming a dropout rate of 10% per year, approximately 300 participants per arm are needed.

Corresponding arms of Cohort 3 and 4 will be combined (Arm 11a [Cohort 3] + Arm 14 [Cohort 4], and Arm 11b [Cohort 3] + Arm 15 [Cohort 4], respectively) for the evaluation of durability of the immune response. Having 75 participants in Arm 11a and 11b in Cohort 3 requires enrollment of 225 participants in Arms 14 and 15 in Cohort 4. Enrollment of 90 participants in Arm 16 (placebo) results in enrollment of in total 540 participants in Cohort 4. Placebo arms from Cohort 3 and 4, Arm 12 and Arm 16, respectively, will be combined in the analyses, as applicable.

Table 17 shows the probabilities of observing at least one AE for the selected formulation for future clinical development, at given true AE rates. This table shows that the current numbers give a reasonable probability to also observe less frequent events in the active arms in this cohort.

**Table 17: Probability of Observing at Least One Adverse Event for the Selected Formulation for Future Clinical Development, at a Given True Adverse Event Rate**

| True AE Rate (%) | Probability of Observing at Least One AE in N Participants (%) |        |        |        |        |
|------------------|----------------------------------------------------------------|--------|--------|--------|--------|
|                  | N=150                                                          | N=225  | N=300  | N=450  | N=600  |
| 0.5              | 52.9%                                                          | 67.6%  | 77.8%  | 89.5%  | 95.1%  |
| 1                | 77.9%                                                          | 89.6%  | 95.1%  | 98.9%  | 99.8%  |
| 2.5              | 97.8%                                                          | 99.7%  | 99.9%  | 100.0% | 100.0% |
| 10               | 100.0%                                                         | 100.0% | 100.0% | 100.0% | 100.0% |
| 25               | 100.0%                                                         | 100.0% | 100.0% | 100.0% | 100.0% |

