#### 5.3.3. Analysis Methods for the Primary Immunogenicity endpoint(s)

For Cohort 1, 2 and 4 the primary endpoint will be RSV neutralization antibody titers measured for RSV-A and RSV-B. In Cohort 3, RSV neutralization antibody titers are a secondary endpoint.

Data of corresponding arms from Cohort 1 and Cohort 2 will be combined in all analyses. Immunogenicity data of corresponding arms from Cohort 3 and Cohort 4 will be combined as applicable, too.

Descriptive statistics will be used for all arms to analyze the actual values (geometric mean, 95% CI, minimum, maximum, median and quartiles) and fold increase from baseline at all timepoints, as well as the percentage of participants with 2- and 4-fold increases from baseline. Additionally, the RSV-A/RSV-B antibody ratio will be reported by time points and the fold increase of RSV-A/RSV-B antibody ratio from baselines will be calculated at all timepoints.

For combined data from Cohort 1 and Cohort 2, geometric mean ratios for each active arm relatively to control Arm 1a and relatively to control Arm 1b, as well as relatively to each other will be calculated at all available timepoints along with corresponding 95% CI as applicable.

For Cohort 3, Arms 11a and 11b will be combined and the active arms (10, 11a+11b, 13) will be compared to each other at all available timepoints up to 1 year after vaccination on Day 1 by calculating the geometric mean ratios along with corresponding 95% CIs.

For durability and revaccination evaluation analyses, the following arms will be combined and compared to each other for all timepoints:

- Arm 11a (Cohort 3) combined with Arm 14 (Cohort 4);
- Arm 11b (Cohort 3) combined with Arm 15 (Cohort 4);
- Arm 12 (Cohort 3) combined with Arm 16 (Cohort 4).

Geometric means per arm of values for RSV-A, RSV-B and the ratio of RSV-A/RSV-B, geometric mean ratios for RSV-A, RSV-B and the ratio of RSV-A/RSV-B between all active arms along with corresponding 95% CIs will be estimated via an analysis of variance (ANOVA) using log-transformed post-vaccination immuno parameter response as dependent variable and study arm as independent variable. The means and differences in mean and CIs will be back transformed (by exponentiation) to CIs around a geometric mean or geometric mean ratio. This analysis will be performed by time points, separately per parameter. As a sensitivity analysis, the ANOVA may also be performed adjusting for baseline titer, age and sex.

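### Five-year durability is estimated visit by visit from whoever is still sampled, although about half of each pooled arm is planned to be lost; a repeated-measures model would use the earlier titres of those who left.

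*SAP*

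**What the plan says.** SAP 5.3.3 obtains geometric means and ratios from an ANOVA of log titre with study arm as the only factor: "This analysis will be performed by time points, separately per parameter". SAP 5.6 adds "Missing immune response data will not be imputed", and SAP 5.1.3 drops out-of-window visits from the per-protocol immunogenicity analysis. Two optional sensitivity analyses exist: the same ANOVA adjusted for baseline titre, age and sex (SAP 5.3.3), and key tables on the full analysis set (SAP Table 2). Neither document specifies a repeated-measures model, or any missing-data sensitivity analysis, for the titres.

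On attrition, Protocol 9.2.4 gives the aim as "To have approximately 150 participants available per arm for evaluating durability of immune response at end of the 5-year study period" and concludes "assuming a dropout rate of 10% per year, approximately 300 participants per arm are needed". The 300 come from pooling two cohorts: "Having 75 participants in Arm 11a and 11b in Cohort 3 requires enrollment of 225 participants in Arms 14 and 15 in Cohort 4". Protocol 6.3 states "Participants who withdraw will not be replaced". Protocol section 3 makes neutralizing titres, including their durability with and without revaccination, the primary objective of Cohort 4.

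**The concern.** Each late-visit estimate rests only on participants with a usable sample at that visit. Someone who leaves after year 2 contributes nothing to the year-5 estimate, although that person's earlier titres say a good deal about what a later titre would have been. This has two consequences.

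- Precision is lost whatever the reason for dropout.
- If people who leave differ in titre from people who stay, the planned plot of GMT over time mixes waning with a change in who is measured.

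The second consequence is plausible but not shown. Blinding stops participants reacting to their arm, but participants are aged 60 and over, may have heart failure, COPD or diabetes (Protocol 5.1), and can leave through death or adverse events (Protocol 7.2). Age and health may go with titre.

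No hypothesis is tested, so no type I error is at stake. The estimates and their intervals are the whole result.

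**Working it through.** **1. The plan's own figure.** Inputs from Protocol 9.2.4: 75 + 225 = 300 per pooled active arm, 10% dropout per year, 5 years, target 150.
- Additive: 150 / (1 - 5 × 0.10) = 300. This reproduces the stated number.
- Compounding: 300 × 0.9^5 = 177 left (41% lost), and only 150 / 0.9^5 = 254 would be needed. The plan therefore used the additive form.
- Pooled placebo-first arm (12 + 16): 50 + 90 = 140 enrolled, leaving 70 (additive) or 83 (compounding).

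**2. Precision as planned.** The SD of 1.3 on the log2 scale comes from Protocol 9.2.2 (Day 29, RSV-A2) and is assumed to hold at year 5. The 95% CI around an observed GMR of 1 is 2^(±t × 1.3 × √(2/n)).
- n = 55: 0.71 to 1.41, matching Protocol Table 14.
- n = 300: 0.87 to 1.16.
- n = 177: 0.83 to 1.21.
- n = 150: 0.81 to 1.23.

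**3. Precision if earlier titres are used.** The documents give no within-person correlation. Assume an autoregressive correlation ρ between successive sampling times (Day 29, Day 183, years 1 to 5) and dropout unrelated to titre. With monotone dropout, the variance of the estimated mean in units of SD² follows V_t = (1 - ρ²)/n_t + ρ²V_(t-1), and the effective n is 1/V_t.

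For ρ = 0.7 and additive dropout, n_t = 300, 285, 270, 240, 210, 180, 150. The effective n runs 300, 292, 280, 258, 231, 202, and the last step is 0.51/150 + 0.49/201.9 = 0.00583, giving 171.6.

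| ρ | Effective n against 150 | Effective n against 177 |
|---|---|---|
| 0.7 | 172 | 194 |
| 0.8 | 186 | 206 |
| 0.9 | 217 | 232 |

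CI width on the log scale falls by 1 - √(150/171.6) = 6.5% up to 1 - √(150/216.8) = 17%. With compounding dropout it falls by about 4% to 13%. SAP Table 4 schedules no Day 365 visit for these arms. Dropping year 1 from the recursion moves each result by no more than about 2.

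**4. Bias in the within-arm GMT.** The link between dropout and titre is also assumed. Simulation with 400,000 participants, 10% per year compounding, autoregressive correlation 0.7 to 0.9, and dropout odds 1.25 to 2 times higher per SD lower previous titre gives a year-5 observed-case bias of 0.06 to 0.295 log2. That is 2^0.06 = 1.04 to 2^0.295 = 1.23, or 4% to 23% too high.

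A separate simulation used 300 per arm, six visits, autoregressive or exchangeable correlation 0.5 to 0.9, and odds of 1.5 or 2. It gave factors of 1.04 to 1.28 with 41% lost and 1.05 to 1.38 with 50% lost. In every one of those settings the maximum-likelihood repeated-measures mean was within about 0.5% of the truth. With dropout unrelated to titre, neither method was biased.

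**5. Bias in the GMR.** With the same titre-driven dropout in both arms and an assumed revaccination effect of 0.5 to 1 log2, the year-5 GMR is off by roughly 0.3% to 6%, mostly towards the null.

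**6. Dropout driven by health rather than titre.** Let dropout odds rise 1.5- to 2-fold per SD of a frailty score correlated -0.1 to -0.3 with titre (assumed). The observed-case year-5 GMT is then about 2% to 9% too high. A repeated-measures model without that score is still about 0.3% to 5% too high.

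**The case against.** The strongest reply is that attrition was planned for. Protocol 9.2.4 enrols 300 precisely so that about 150 remain, and that number is reached without any modelling. The study is descriptive, observed-case GMTs are a legitimate description of those sampled, and within-person fold increases and spaghetti plots are also planned. All this stands, and it is why the point is an improvement and not a correction of an error. It does not explain why titres already collected should be left out of the estimates for a primary objective. Neither optional sensitivity analysis uses intermediate titres.

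Four further objections narrow the point.

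- **Direction.** A reader might infer that the plan overstates durability. The documents do not support that. Nothing in them says low titre predicts leaving, and the opposite pattern would understate durability.
- **Comparisons.** A reader might infer that the revaccination GMR is unreliable. Arms are randomised and blinded, so a shared dropout mechanism largely cancels (step 5).
- **Remedy.** The model is not a cure. It corrects only dropout explained by observed data (step 6), and it implicitly projects titres beyond death unless the estimand says otherwise.
- **Feasibility.** SAP Table 4 has 13 post-baseline immunogenicity visits for these arms, so an unstructured covariance has 13 × 14 / 2 = 91 parameters. The visits run on two clocks, and the order of the post-revaccination visits relative to Day 730 is unknown until Day X is fixed.

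Also, the no-imputation rule is not itself the fault. It would remain true under a likelihood-based model.

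**Conclusion.** The point holds as a worthwhile, inexpensive improvement. The plan expects to lose about 50% of each pooled durability arm on its own additive arithmetic (41% if compounding), and its per-visit method sets aside the earlier titres of those who leave.

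The precision gain does not need informative dropout, but its size rests on the assumed correlation: at 0.7 to 0.9, year-5 effective n is 172-217 instead of 150, or 194-232 instead of 177. The bias figure of 4% to 23% for the year-5 GMT is conditional on titre-driven dropout of the assumed strength with 41% lost. It is larger if half are lost, smaller if dropout follows health only loosely tied to titre, and nil if dropout is unrelated to titre. These figures are illustrations, not estimates of what will happen in this trial. The exposure lies mainly in the within-arm GMT curve and much less in the between-arm ratios.

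**What to change.** For the durability and revaccination analyses, add to SAP 5.3.3 a likelihood-based repeated-measures model on log titre with arm, visit, arm-by-visit, baseline titre, age, sex and cohort. Prespecify:

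- a restricted visit set, for example Day 29, Day 183, Day X, X+28, X+182 and Days 730, 1095, 1460 and 1825, ordered once Day X is fixed (9 visits, so 9 × 10 / 2 = 45 covariance parameters instead of 91);
- unstructured covariance, with a named fallback structure if it does not converge;
- a statement that the model assumes dropout depends only on observed data, and how titres after death are treated.

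Keep the per-visit ANOVA alongside it, so that readers can see whether the two agree. The cost is SAP text and programming, with no new visits, samples or participants. The downsides are possible non-convergence and reliance on the missing-at-random assumption.

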### **5.7. Other Safety Analyses**

The analysis of Adverse Events is described in Section 5.3.2. Other safety analyses include laboratory tests, vital signs and physical examination data. All these safety analyses will be based on the FAS using actual intervention received, unless otherwise specified. All the summary tables will be presented by cohort (or pooled over cohorts, as applicable) and study arm, and by group (cohort 1), as applicable.

For all continuous safety variables, descriptive statistics will include the N, mean, standard deviation, median, minimum, maximum, and interquartile range. Categorical variables will be summarized using frequency counts and percentages.

### **5.7.1. Clinical Laboratory Tests**

Laboratory abnormalities will be determined according to the FDA toxicity grading tables (see Appendix 6 of CTP), or in accordance with the normal ranges for the clinical laboratory parameter: any laboratory value shown as a “graded” value in the FDA table that is within laboratory normal ranges will not be graded for severity. All the abnormalities will be summarized and listed.

### **5.7.2. Vital Signs**

Vital signs including temperature, heart rate, respiratory rate, and blood pressure (systolic and diastolic) will be summarized over time, using descriptive statistics and/or graphical representations. The percentage of participants with values beyond clinically important limits will be summarized. Baseline and emerging vital sign abnormalities will be listed based on the abnormality gradings in Appendix 6 of the CTP. An abnormality will be considered as emerging if it is worse than the baseline value. If the baseline is missing, the abnormality is always considered emerging.

### **5.7.3. Physical Examinations**

Physical examination findings pre-vaccination will be summarized per vaccine administration. A summary table as well as listing of the abnormalities will be presented.

## **5.8. Other Analyses**

### **5.8.1. Pharmacokinetics**

Not applicable.

### **5.8.2. Pharmacodynamics**

Not applicable.

### **5.8.3. Biomarkers**

Biomarker data analysis may be conducted at the sponsor’s discretion and may be detailed and reported separately.

### **5.8.4. Definition of Subgroups**

No subgroup analysis is planned for this study.

## **5.9. Planned Analyses**

The following analyses are planned:

- Primary analysis: 28 days post-vaccination safety and immunogenicity analysis up to D15 for humoral antibodies. This analysis will be performed when all participants in Cohort 1 and Cohort 2 have completed their 28-day post-vaccination visit. For primary analysis humoral immunogenicity will include baseline and Day 15 data, while safety analysis will be included the data up to Day 29 visit. Data from corresponding arms from the two cohorts will be combined. The goal of this analysis will be to select the vaccine formulation to be used in Cohort 3.

- Interim analyses:
  - 84 days post-vaccination immunogenicity analysis for Cohorts 1 and 2. Available immunogenicity data of all participants in Cohort 1 and Cohort 2 up to the Day 85 will be included in the analysis. 6-month post-vaccination safety and immunogenicity analysis for Cohorts 1 and 2. Available safety and immunogenicity data of all participants in Cohort 1 and Cohort 2 up to the Day 185 follow-up visit post-vaccination will be included in the analysis. This analysis may include immunogenicity data available from additional timepoints.
  - 1-year post-vaccination immunogenicity analysis for Cohorts 1 and 2. Immunogenicity data of all participants in Cohort 1 and Cohort 2 up to (and including) the 1-year follow-up visit post-vaccination will be included in the analysis.
  - 28 days post-vaccination safety and immunogenicity analysis for Cohort 3. This analysis will be performed when all participants in Cohort 3 have completed their 28-day post-vaccination visit.
  - 28 days post-vaccination safety and immunogenicity analysis for Cohort 4. This analysis will be performed when all participants in Cohort 4 have completed their 28-day post-vaccination visit.
  - 6-month post first vaccination safety and immunogenicity analysis for Cohorts 3 and 4. This interim analysis will include all safety and immunogenicity data from all participants in Cohorts 3 and 4, collected up to (and including) the 6-months follow-up visit post Day 1 vaccination.
  - 28 days post revaccination safety and immunogenicity analysis for Cohorts 3 and 4. This interim analysis will include all safety and immunogenicity data from all participants in Cohorts 3 and 4, collected up to (and including) the 28-day post-revaccination visit.
  - Yearly follow-up analyses until 3 years post first vaccination in Cohorts 1 and 2 and until 5 years post first vaccination in Cohort 3 (Arms 11a, 11b and 12) and Cohort 4. These analyses will include immunogenicity and safety data up to the 2-year follow-up visit post Day 1 vaccination, the 3-year follow-up visit post Day 1 vaccination, the 4-year follow-up visit post-Day 1 vaccination (applicable for Cohort 3 [Arms 11a, 11b and 12] and Cohort 4 only), and 5-year follow-up visit post Day 1 vaccination (applicable for Cohort 3 [Arms 11a, 11b and 12] and Cohort 4 only).
- Final analysis: immunogenicity analysis and safety data up to study end.

Additional interim analyses may be performed during the study for the purpose of informing future vaccine development-related decisions in a timely manner, or upon health authority request. If they occur, these unplanned interim analyses may replace or be combined with planned analyses, depending on the timing.

For any planned or additional analysis performed before the final analysis, the sponsor will be unblinded at the time of the analysis, while study site personnel and participants will remain blinded until the end of the study.

